### **6.3.9. Electrocardiograms**

A single 12-lead ECG will be obtained at screening/baseline (Table 9). A single 12-lead ECG will also be obtained before blood draws (pre-dose) and 60 to 90 minutes after the end of infusion on Day 1/Week 1, and Weeks 5, 13, 25, 49, and EOS/ET (Table 9). The ECG must be performed after the participant has been resting (supine) for at least 10 minutes.

All ECG tracings will be reviewed locally for safety by the Investigator or a qualified designee. Heart rate, QRS, corrected QT interval by Fredericia (QTcF), RR interval, and result interpretation will be captured in the eCRF.

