- g. Perform/collect prior to dosing. For all post-screening MRIs, the MRI should occur at least 5 days prior to the next dose administration and no more than 10 days prior to the next dose administration, with results received from the central imaging vendor prior to dosing. Note that the central imaging vendor typically requires 5 business days after receipt of the MRI before sending a BMW to the site. MRIs may be scheduled outside of the prescribed window, with approval from the Medical Monitor. The Sponsor may request that additional unscheduled MRIs be performed for the detection and follow-up of ARIA. Participants with MRI evidence of ARIA should be managed according to instructions provided in [Table 8](#).
- h. Vital signs include temperature, respiratory rate, pulse rate, and systolic and diastolic BP while the participant is at rest in a supine position for at least 3 minutes. Heart rate and BP measurements should be obtained with a validated digital monitoring device where available and an appropriately sized cuff. The same arm should be used for all BP measurements if possible. Heart rate and BP should not be measured unless 15 minutes have passed since the last blood draw.
- i. Perform/collect prior to dosing, and at the end of the infusion. Vital signs will be collected and concomitant medications and AEs documented prior to and at the end of infusion. On dosing visits, serum PK samples will be collected pre-dose. On non-dosing visits, serum PK samples may be collected at any time during the visit. Blood samples for assessment of ADA will be taken throughout the study.
- j. Urine pregnancy test (WOCBP only) and vital signs will be performed, and concomitant medications and AEs will start being collected at the screening/baseline visit and subsequent visits for those participants participating in a Tau PET scan.
- k. Complete PE includes evaluation of the head, eyes, ears, nose, and throat, and the cardiovascular, dermatological, musculoskeletal, respiratory, and gastrointestinal systems. Breast, rectal, and genitourinary exams should be performed as clinically indicated. Limited exams should include cardiovascular, respiratory, and gastrointestinal systems. Symptom-directed PEs may also include any other pertinent system as required.
- l. Neurological examination includes an evaluation of consciousness, orientation, cranial nerves, motor and sensory system, coordination and gait, and reflexes.

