- m. Perform a limited, symptom-directed PE at specified timepoints or as clinically indicated.
- n. Includes any medication (eg, prescription drugs, herbal or homeopathic products, vitamins, minerals, vaccines, topical medications, and over-the-counter medications) used by a participant from 14 days prior to initiation of study drug to the final study visit.

- o. AEs, AESIs, and SAEs will be assessed after the participant signs the informed consent until the EOS participation. Any unresolved AEs, AESIs, and SAEs will be followed up through resolution or return to baseline. Additionally, SAEs considered related to study drug or [F]MK-6240 radiotracer, which occur at any time during the study, will be reported until resolution, participant withdrawal of consent, loss to follow-up, or death, whichever is applicable. Definitions describing what is and is not considered an AE are provided in [Section 7](#).
- p. A single 12-lead ECG will be obtained before blood draws (pre-dose) on appropriate days. A single 12-lead ECG will be performed pre-dose and 60 to 90 minutes after the end of infusion on Day 1/Week 1, Weeks 5, 13, 25, and 49. The ECG must be performed after the participant has been resting (supine) for 10 minutes.
- q. Hematology includes hemoglobin, hematocrit, mean corpuscular hemoglobin, mean corpuscular volume, mean corpuscular hemoglobin concentration, white blood cells, red blood cells, platelet count, and differential count (neutrophils, lymphocytes, monocytes, basophils, eosinophils, and other cells).
- r. Chemistry panel (serum or plasma) includes sodium, potassium, chloride, calcium, glucose, bicarbonate, albumin, total protein, creatinine, hemoglobin A1c, blood urea nitrogen or urea, aspartate aminotransferase, alanine aminotransferase, gamma glutamyl transpeptidase, alkaline phosphatase, phosphorus, total bilirubin (direct and indirect), amylase, cholesterol (total, low-density lipoprotein, high density lipoprotein), triglycerides, uric acid, creatine phosphokinase, lactate dehydrogenase, magnesium, and C-reactive protein.
- s. Coagulation panel includes prothrombin time with international normalized ratio, activated partial thromboplastin time. If the LP is required for the EOS, the coagulation panel will be performed at the visit immediately preceding the EOS Visit within 4 weeks ±5 days.

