3.2 Participant Grouping

There are two treatment classes for the LTE and Integrated Analyses:

- **Group T-T** includes participants who were exposed to AL002 during the Core Study. They will continue at their Core Study AL002 dosage during the LTE Study if enrolled in the LTE Study. Group T-T is further broken down as AL002 15 mg/kg, 40 mg/kg, and 60 mg/kg treatment groups.

- **Group P-TC** includes participants who were exposed only to placebo during the Core Study. They will be assigned to the TC during the LTE Study if enrolled in the LTE Study. Group P-TC might be separated into placebo and TC treatment groups depending on the summaries/analyses.

For Group P-TC, the data collected when the participants were receiving placebo in the Core Study might be summarized and/or analyzed separately from the data collected once the participants received the first study drug administration in the LTE Study. The data collected when the participants were receiving placebo in the Core Study up to the day before the participants received the first study drug administration in the LTE Study (separately from the data collected in the LTE Study) is referred to as **the Placebo Data** throughout the SAP. And it includes the data from the placebo participants who did not enroll in the LTE Study. The data collected on or after the day when the participants received the first study drug administration in the LTE Study is referred to as **the TC Data** throughout the SAP.

The first dose date of AL002 refers to the earliest date of any amount of AL002 administered across the Core Study and the LTE Study. **The last dose date of AL002** refers to the latest date of any amount of AL002 administered across the Core Study and the LTE Study. **The first dose date of any study drug** refers to the earliest date of any study drug administered, including placebo, across the Core Study and the LTE Study.

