| Week 48 | 337 | [254, 449] | [254, min (449, LTE Day1)] |
| Week 80 | 561 | [450, 617] | [450, min (617, LTE Day 1)] |
| Week 96 | 673 | [618, 687] | [618, min (687, LTE Day 1)] |
| Week 100 | 701 | [688, 715] | [688, LTE Day 1] |
| Week 104 | 729 | [716, 757] | |
| Week 112 | 785 | [758, 827] | |
| Week 124 | 869 | [828, 953] | |
| Week 148 | 1037 | [954, 1065] | |
| Week 156 | 1093 | > 1065 | |

^a Target Day and Core Study Day are based on Core Study Day 1.

^b When assigning an analysis visit, also assign relative time as Predose or Post-infusion, which should correspond to Predose or Post-infusion as specified in Section 7.1.4.2.

^c LTE Day 1 represents Core Study Day of first dose date of LTE Study. If no such date, use Core study day of the last visit date among Core visits and LTE screening visit.

Table 7-8. Analysis Visit Windows for ECG Assessments Based on LTE Study Day ^a

| Analysis Visit ^b | Target Day | Analysis Visit Window |
|-----------------------------|------------|-----------------------|
| LTE Baseline | 1 | ≤ 1 |
| LTE Week 4 | 29 | [2, 57] |
| LTE Week 12 | 85 | [58, 127] |
| LTE Week 24 | 169 | [128, 253] |
| LTE Week 48 | 337 | [254, 365] |
| LTE Week 56 | 393 | > 365 |

^a Target Day and LTE Study Day are based on LTE Study Day 1.

^b When assigning an analysis visit, also assign relative time as Predose or Post-infusion, which should correspond to Predose or Post-infusion as specified in Section 7.1.4.2.

Table 7-9. Analysis Visit Windows for Weight Based on Core Study Day ^a

| Analysis Visit | Target Day | T-T Analysis Visit Window | Placebo Analysis Visit Window ^b |
|----------------|------------|---------------------------|--|
| Core Baseline | - | ≤ 1 | ≤ 1 |
| Week 4 | 29 | [2, 43] | [2, 43] |
| Week 8 | 57 | [44, 71] | [44, 71] |
| Week 12 | 85 | [72, 99] | [72, 99] |
| Week 16 | 113 | [100, 127] | [100, 127] |
| Week 20 | 141 | [128, 155] | [128, 155] |
| Week 24 | 169 | [156, 183] | [156, 183] |
| Week 28 | 197 | [184, 211] | [184, 211] |
| Week 32 | 225 | [212, 239] | [212, 239] |
| Week 36 | 253 | [240, 267] | [240, 267] |
| Week 40 | 281 | [268, 295] | [268, 295] |
| Week 44 | 309 | [296, 323] | [296, 323] |
| Week 48 | 337 | [324, 351] | [324, min (351, LTE Day 1)] |
| Week 52 | 365 | [352, 379] | [352, min (379, LTE Day 1)] |
| Week 56 | 393 | [380, 407] | [380, min (407, LTE Day 1)] |
| Week 60 | 421 | [408, 435] | [408, min (435, LTE Day 1)] |
| Week 64 | 449 | [436, 463] | [436, min (463, LTE Day 1)] |

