7.1.4.2 Handling of Predose and Post-infusion

For vital signs and ECG data that collect measurements at multiple time points (predose, post-infusion, or “Not Applicable”) on a study drug administration day, the following rules apply for assigning the measurements to times, when applicable.

(1) For the assessments collected on Study Day 1:

- The entries on the corresponding electronic CRF (predose, post-infusion) will be used.
 - If the entry on the corresponding electronic CRF is “post-infusion”, the assessment will be assigned the analysis visit “Day 1 Postdose”. Measurement time points are not applicable for “Day 1 Postdose”.
 - If the entry on the corresponding electronic CRF is “predose”, it will be considered as a candidate for baseline, and the baseline selection rules apply. Measurement time points are not applicable for baseline.

(2) For assessments collected at a post-Study-Day-1 scheduled visit, in which study drug is administered per the Schedules of Assessments in the protocols, the entries on the corresponding electronic CRF (predose, post-infusion) will be used, if the date of assessment is prior to or on the last dose date.

(3) For post-Study-Day-1 visits at which study drug is not administered per the Schedules of Assessments in the protocols, including Week 3 (vital signs only), Unscheduled, EFU, SFU, and ET, “Not Applicable” will be assigned as the measurement time point.

(4) For assessments collected after the last dose date, “Not Applicable” will be assigned as the measurement time point. And this takes precedence over entries on the corresponding electronic CRF.

(5) For assessments collected prior to the first dose date, time points do not apply. And this takes precedence over entries on the corresponding electronic CRF.

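### The placebo windows for ECG and vital signs include the day of the first AL002 infusion, contrary to SAP 3.2, and the Titration Cohort tables have no row for post-infusion readings on that day

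*SAP*

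**What the plan says.** **Where Placebo Data end.** SAP 3.2 takes the Placebo Data "up to the day before the participants received the first study drug administration in the LTE Study" and starts the Titration Cohort (TC) Data on the dosing day itself.

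**Where the placebo windows end.** In Tables 7-7 and 7-10 the last placebo row is "Week 100 | 701 | [688, 715] | [688, LTE Day 1", inclusive. The footnote to both tables explains: "LTE Day 1 represents Core Study Day of first dose date of LTE Study". Earlier rows (from Week 48 on) are capped at the same day, also inclusively.

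**What is measured that day.** Protocol 6.3.9 asks for an ECG before dosing and again "60 to 90 minutes after the end of infusion on Day 1/Week 1"; Table 9 footnote p repeats this. For vital signs, footnote i says: "Vital signs will be collected and concomitant medications and AEs documented prior to and at the end of infusion".

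**Where post-infusion readings go.** SAP 7.1.2.2, part of the LTE baseline rules, bars post-infusion values on Study Day 1 from baseline and assigns them to *Day 1 Postdose*, pointing to Tables 7-7 and 7-10. SAP 7.1.4.2(1) gives the same assignment for Study Day 1 without saying whether Core or LTE is meant. Rule (2) covers later dosing visits: "For assessments collected at a post-Study-Day-1 scheduled visit, in which study drug is administered per the Schedules of Assessments in the protocols". There the predose or post-infusion entry on the eCRF is used.

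**The LTE-clock tables.** Table 7-8 (ECG) has LTE Baseline at ≤ 1, then LTE Week 4 at [2, 57]. Table 7-11 (weight and vital signs) has LTE Baseline at ≤ 1, then LTE Week 4 at [2, 43].

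**The concern.** Changes in ECG and vital signs are primary safety endpoints (SAP Table 2-1, Part 2), and the placebo data are the only untreated comparator in the integrated safety tables. A window that admits the first AL002 infusion day with no predose limit can put readings taken on active drug into that comparator.

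The tables already use the right device elsewhere. At Core Day 1, Tables 7-7 and 7-10 limit baseline to predose and add a *Day 1 Postdose* row. At the next first-dose event, LTE Day 1, neither safeguard appears.

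The Titration Cohort has the complementary problem. Its first post-infusion ECG and vital signs are the readings most directly informative about acute effects of first exposure, and they can drop out of the by-visit tables for the group they describe.

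**Working it through.** No power or sample-size figure is involved. The check is to place an LTE Day 1 reading under each rule.

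**Inputs**
- Week 96 target: Core Day 673 (Tables 7-7 and 7-10).
- Gap from last Core dose to first LTE dose: 28 ± 5 days (SAP 3.1).
- Placebo Week 100 window: Core Day 688 to LTE Day 1.
- Assumption: the last Core dose of a 96-week completer falls at the Week 96 target, ± 5 days, so Day 668 to 678. The documents supplied do not give the Core visit window.

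**Step 1: where LTE Day 1 falls.** LTE Day 1 = last Core dose + 28 ± 5.

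| Last Core dose | LTE Day 1 at −5 / 0 / +5 days |
|---|---|
| 668 | 691 / 696 / 701 |
| 673 | 696 / 701 / 706 |
| 678 | 701 / 706 / 711 |

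The central value is 673 + 28 = 701, the Week 100 target. SAP 7.1.1.2.2 agrees: it pairs Week 104 with LTE Week 4, so LTE Day 1 corresponds to Week 100, and 100 × 7 + 1 = 701.

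**Step 2: windows alone.** A reading on LTE Day 1 is in placebo Week 100 if 688 ≤ LTE Day 1, because the upper bound is LTE Day 1 itself. The smallest value is 691, so all 9 combinations fall in Week 100, for ECG and for vital signs. When LTE Day 1 is Day 701, the reading is at distance zero from target, and the closest-to-target rule in SAP 7.1.3.2 selects it.

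**Step 3: SAP 3.2.** With the upper bound at LTE Day 1 minus 1, the same reading falls in no placebo window in any of the 9 combinations. The two rules give opposite answers.

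**Step 4: Titration Cohort tables.** LTE Study Day 1 matches only LTE Baseline (≤ 1) in Tables 7-8 and 7-11. SAP 7.1.2.2 excludes post-infusion values from baseline and sends them to a row that exists only in the Core tables, where its target is Core Day 1. A footnote to Table 7-8 calls for a predose or post-infusion label, but 7.1.4.2(1) says time points do not apply to baseline. No by-visit row is left.

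**Step 5: the label if the reading is kept as placebo.** On the Core clock this is a dosing visit after Study Day 1, so rule (2) of 7.1.4.2 would keep the post-infusion label. Rule (4) instead labels anything after the last dose date as not applicable and overrides the eCRF entry. SAP 6.2.1 ties the placebo dose dates to the Core Study. If that date is meant, the predose and post-infusion readings of LTE Day 1 share one label, and 7.1.3.2 averages same-day continuous values. Rule (4) does not say which last dose date it uses.

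**The case against.** The strongest reply is that the SAP already keeps these readings out of placebo. SAP 7.1.1.2.1 says the Core-clock weeks apply to the Placebo Data as SAP 3.2 defines them, and the LTE-clock weeks to the TC Data. If the data are split first and the windows applied afterwards, a reading on LTE Day 1 is TC Data and cannot be placebo. SAP 7.1.2.2 sits among the LTE baseline rules, and 7.1.4.2(1) is not limited to Core, so *Day 1 Postdose* can be read as covering LTE Study Day 1. What is missing is then a table row, not a rule.

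Much of this stands. A reader might infer that post-AL002 readings definitely are tabulated as placebo, or that the placebo Week 100 post-infusion cell consists of nothing else. The documents support neither. SAP 3.2 points the other way, and under rule (4) the readings may carry the not-applicable label. The QTcF and ECG-criteria summaries in SAP 7.4.6 use only predose and post-infusion, so such records would not enter them.

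Two further limits stand. For participants who roll over earlier, a Core reading near the visit target would usually be selected over a later LTE Day 1 reading. Also, the first titration dose is 2 or 6 mg/kg (SAP 3.1), the summaries are descriptive, all readings are listed, and nothing in the documents shows an acute ECG or vital-sign effect.

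The reply does not remove the contradiction. SAP 7.1.1.2 says both sets of windows will be implemented, and no rule says which prevails when a printed bound disagrees with SAP 3.2. The gap in Tables 7-8 and 7-11 remains on every reading.

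**Conclusion.** The finding is an internal contradiction plus a missing row. The placebo windows in Tables 7-7 and 7-10 extend one day beyond the Placebo Data of SAP 3.2, and post-AL002 readings are scheduled on that extra day. Applied as printed, the windows can place those readings in placebo: in Week 100 for a 96-week completer, under the assumption on the last Core dose. Independently of this, the Titration Cohort's LTE Day 1 post-infusion readings have no by-visit row.

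The exposure is at most one post-infusion ECG and one post-infusion vital-sign set per former placebo participant. The placebo share of LTE enrollment is not stated. If it were one quarter to one third of the 176 to 198 expected (SAP 3.5), that would be 176/4 = 44 to 198/3 = 66 participants. This is an illustration only.

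Misplaced readings can raise placebo outlier counts, notably in the overall rows of SAP 7.4.6 and 7.4.7, which take the most severe record. It would go too far to say that they do raise them: that depends on which rule the programmer follows and on whether there is an acute effect. The point is worth correcting because it touches primary safety endpoints and their only untreated comparator.

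**What to change.** 1. Use one cut that excludes post-AL002 readings. Either write *LTE Day 1 predose* into both the placebo bounds of Tables 7-7 and 7-10 and SAP 3.2, or leave SAP 3.2 as it is and set the bounds to LTE Day 1 minus 1. The first keeps the LTE Day 1 predose reading in placebo. Under the second that reading serves only as LTE baseline, and for a completer with LTE Day 1 on Day 701 the placebo Week 100 row holds only readings from Day 688 to 700.
2. Add an *LTE Day 1 Postdose* row to Tables 7-8 and 7-11, and limit their LTE Baseline to predose for measurements with a recorded time point.
3. Cite Tables 7-8 and 7-11 in SAP 7.1.2.2.
4. State in SAP 7.1.4.2 that Study Day 1 includes LTE Study Day 1 for Group P-TC, and which last dose date rule (4) uses.

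The cost is SAP wording, one added row in each of two tables, and the matching programming. The eCRF already records predose and post-infusion, so no new data are needed.

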### **1.2.2. Clinical Studies**

Study AL002-1 assessed the safety, tolerability, PK, and pharmacodynamics (PD) of IV administration of AL002 administered as a single-dose to healthy volunteers as well as multiple doses to participants with mild to moderate AD. Study AL002-1 was closed to enrollment by Alector on 14 May 2020 given the available data already obtained and limitations on enrollment due to the coronavirus disease 2019 (COVID-19) pandemic.

AL002 was studied in 64 healthy volunteers enrolled in the first portion of the AL002-1 study, which evaluated single-dose IV infusion administration of AL002 with doses ranging from 0.003 to 60 mg/kg. All participants in these single-ascending dose cohorts reached the end of their dose-limiting adverse event (DLAE) assessment windows. Fifty-three participants were exposed to AL002, and 11 participants were on placebo. All participants have completed the study, with the exception of 1 participant (60 mg/kg), who withdrew consent after receiving one dose of AL002. The second portion of AL002-1 evaluated AL002 administered in multiple doses in participants with AD. Due to the closing of enrollment, only 5 of the planned 32 participants with AD were enrolled in the multiple dosing part. Three participants (2 on AL002 and 1 on placebo) were enrolled on a schedule that evaluated AL002 15 mg/kg weekly for 4 doses. Following a protocol amendment, an additional 2 participants (1 on AL002 and 1 on placebo) were enrolled on a schedule that evaluated AL002 60 mg/kg every 4 weeks for 2 doses. In this study, there were no deaths, no DLAEs, no treatment-related serious adverse events (SAEs), and no adverse events of special interest (AESIs). One participant in the pooled placebo group had a Grade 3 injury (attributed to trauma) that was serious and was considered unrelated to study drug. Two participants in the single-ascending dose part experienced adverse events (AEs) considered probably related to AL002 that led to withdrawal of study drug. Overall, AL002 was considered generally safe and well tolerated in this trial.

In the ongoing, randomized, double-blind, placebo-controlled, dose-ranging Phase 2 study, AL002-2, the AL002 is administered for up to 96 weeks via IV infusion every 4 weeks. To

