Analysis visit windows for efficacy parameters are defined in a similar manner as those for safety and PK data. Efficacy data will be summarized based on the analysis visits (hereinafter may be referred to as “visit”), when applicable.

For efficacy data, the analysis visits will be in the format of “Week y/LTE Week x” when applicable, where “LTE Week x” refers to the analysis visits based on LTE Study Day for Group P-TC, “Week y” refers to the analysis visits based on Core Study Day for Group T-T (e.g. Week 104/LTE Week 4, Week 156/LTE Week 56). For data during the Core study, Group T-T and Group P-TC will have the label “Week x”. For the TC, “LTE Week x” will be abbreviated and displayed as “Week x” for the TC, and shown along with “Week x” values of Group T-T.

Table 7-26. Analysis Visit Windows for Efficacy Assessments Based on Core Study Day^a

| Nominal Visit per Protocol | Target Day | Analysis Visit | T-T Analysis Visit Window | P-TC Analysis Visit Window ^d |
|----------------------------|------------|----------------------------|---------------------------|---|
| Screening Phase | | | | |
| Screening | - | Core Baseline ^c | ≤ 1 | ≤ 1 |
| Treatment Phase | | | | |
| Week 1 ^b | 1 | | | |
| Week 25 | 169 | Week 24 | [2, 253] | [2, 253] |
| Week 49 | 337 | Week 48 | [254, 421] | [254, min (421, LTE Day 1)] |
| Week 73 | 505 | Week 72 | [422, 589] | [422, min (589, LTE Day 1)] |
| Week 97 | 673 | Week 96 | [590, 771] | [590, LTE Day 1] |
| Week 125 | 869 | Week 124 | [772, 953] | LTE Week 24 |
| Week 149 | 1037 | Week 148 | > 953 | LTE Week 48 |

^a Target Day and Core Study Day are based on Core Study Day 1.

^b COAs are scheduled to be performed/collected prior to dosing.

^c Baseline for efficacy is defined in Section [7.1.2](#).

^d LTE Day 1 represents Core Study Day of first dose date of LTE Study. If no such date, use Core study day of the last visit date among Core visits and LTE screening visit. LTE Weeks are from [Table 7-27](#).

Table 7-27. Analysis Visit Windows for Efficacy Assessments Based on LTE Study Day^a

| Nominal Visit per Protocol | Target Day | Analysis Visit | Analysis Visit Window |
|----------------------------|------------|----------------|-----------------------|
| LTE Day 1 | 1 | LTE Baseline | ≤ 1 |
| LTE Week 25 | 169 | LTE Week 24 | [2, 253] |

| | | | |
|-------------|-----|-------------|-------|
| LTE Week 49 | 337 | LTE Week 48 | ≥ 254 |
|-------------|-----|-------------|-------|

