7.6.1 Descriptive Summaries of Efficacy Endpoints

The integrated descriptive summary of an efficacy endpoint including the Placebo Data will summarize all the data collected in the Core Study and in the LTE Study with descriptive statistics, by individual placebo/TC, AL002 15 mg/kg, 40 mg/kg, and 60 mg/kg, and the TC treatment groups, and AL002 40 and 60 mg/kg combined group.

The CFB and PCFB will be based on the Core baseline for placebo/TC, AL002 15 mg/kg, 40 mg/kg, and 60 mg/kg, and AL002 40 and 60 mg/kg combined treatment groups. The CFB and PCFB for the TC will be based on the LTE baseline. And all analysis visits from the Core and LTE Studies will be included.

Longitudinal trend (line-plot) figures (group mean [unadjusted] of change from Core baseline \pm SEM (standard error of the mean) over time at each analysis visit) over the Core + LTE periods for placebo/TC, AL002 15 mg/kg, 40 mg/kg, and 60 mg/kg treatment groups will be created.

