7.6.2 Analyses of Efficacy Endpoints

For Integrated Analysis, the analyses as described in the Core Study SAP will be repeated based on the integrated data up to Week 96 since the initiation of study treatment from both the Core Study and the LTE study for the AL002 treatment groups and the data from the Core Study and the screening visit of LTE study for the placebo treatment group. This includes the fitting of MMRM and pMMRM models, to obtain estimates of least square mean difference in CFB and percent slowing of decline (from MMRM) and proportional treatment effect (from pMMRM).

A pMMRM approach (G. Wang et al., 2022) will be used as the primary analysis of all efficacy endpoints. Conceptually, the pMMRM is similar to the Cox proportional hazards model, as it models the treatment effect as a single proportional difference at each post-baseline visit. It uses time as a categorical variable like an MMRM and thus avoids the linearity assumption. On the other hand, pMMRM takes on the assumption of a proportional treatment effect of a linear mixed-effect (LME) model and thus uses assessments more efficiently than an MMRM model.

A restricted maximum likelihood based MMRM will be used as a supportive analysis to assess the primary endpoint. The SAS® MIXED procedure will be used to fit an MMRM with CFB in CDR-SB at each scheduled post-baseline visit (Week 24, 48, 72, and 96) as the dependent variables and the fixed effects will include following items:

- Treatment group,
- Visit (categorical, as week),
- Visit-by-treatment interaction,
- Core Baseline CDR-SB score (covariate),
- APOE e4 status (covariate, e4 carrier vs non-e4 carrier).

An unstructured covariance matrix will be used to model within-participant variance-covariance errors. If the unstructured covariance structure matrix results in a lack of convergence, the following tests will be used in sequence:

- Heterogeneous Toeplitz (TOEPH) covariance structure,
- Heterogeneous first-order autoregressive (ARH(1)) covariance structure,
- Heterogeneous compound symmetry (CSH) covariance structure,
- Toeplitz (TOEP) covariance structure,
- First-order autoregressive (AR(1)) covariance structure,
- Compound symmetry (CS) covariance structure.

In the case that a structured variance-covariance matrix is used to enable the model to converge, the "sandwich" estimator of the variance-covariance matrix will be employed by using the "empirical" option in the SAS PROC MIXED procedure.

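### In the Core-baseline displays after Week 96, placebo/Titration Cohort visits are placed by extension day and AL002 visits by Core day, so visits of early roll-overs appear up to about 48 weeks later than they occurred

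*SAP*

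**What the plan says.** SAP 7.1.1.2.2 uses two clocks for efficacy visits after roll-over. The LTE week "refers to the analysis visits based on LTE Study Day for Group P-TC", while the Core week "refers to the analysis visits based on Core Study Day for Group T-T (e.g. Week 104/LTE Week 4, Week 156/LTE Week 56". Those examples fix an offset of 100 weeks.

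Table 7-26 applies the rule in its last two rows, "Week 125 | 869 | Week 124 | [772, 953] | LTE Week 24" and "Week 149 | 1037 | Week 148 | > 953 | LTE Week 48". The fourth entry in each row is the Core-day window for Group T-T. The fifth is the entry for Group P-TC, and it points to Table 7-27, where the window is counted from the first extension dose: "LTE Week 25 | 169 | LTE Week 24 | [2, 253]".

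The same pairing is used for volumetric MRI (Table 7-12), plasma (7-28), CSF (7-30), amyloid PET (7-32) and tau PET (7-34 and 7-36).

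SAP 7.6.1 and 7.7.2 then tabulate change from Core baseline and plot the "group mean [unadjusted] of change from Core baseline" at each analysis visit, with placebo/TC beside the 15, 40 and 60 mg/kg groups across Core and LTE.

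On the length of Core treatment, Protocol 1.2.2 says "the AL002 is administered for up to 96 weeks via IV infusion every 4 weeks". Protocol 3.2.2 puts the first LTE dose 4 weeks, plus or minus 5 days, after the last Core dose.

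**The concern.** A plot of change from Core baseline invites the reader to compare groups at equal time since baseline. Here the label Week 124 means a range of Core days for Group T-T, but 24 weeks after the switch for Group P-TC, whatever the length of Core treatment. Two participants with identical dates can get different labels purely because of their arm.

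Alzheimer's disease is progressive. If some placebo participants switch before Week 100, their post-switch points carry less elapsed time than the label says, and hence less decline on measures that worsen steadily. The placebo/TC line would look better against the continuously treated groups than it should, and a real advantage of starting AL002 earlier could be hidden. The models stop at Week 96, so these displays are the only comparison of placebo/TC with the AL002 doses from Core baseline after that point.

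**Working it through.** **Reproducing the SAP pairing.** From the definitions in SAP 7.1.1.1, Core Study Day = (Core Study Day of LTE Day 1) + LTE Study Day − 1. A last Core dose at Week 96 is Day 673. Adding 28 days gives LTE Day 1 = Core Day 701.

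- LTE Week 24, Day 169: 701 + 168 = 869, the Table 7-26 target for Week 124.
- LTE Week 48, Day 337: 701 + 336 = 1037, the target for Week 148.

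Both are exact, so the gap is zero for a full-duration participant on schedule.

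**Is earlier roll-over allowed for?** Three places point that way.

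- Core dosing has a maximum of 96 weeks, not a fixed length.
- The P-TC windows are cut at LTE Day 1 from the Week 48 row of Table 7-26. In the 4-weekly weight and vital-signs tables the cut also starts at Week 48. It would do nothing in the Week 48 and Week 72 rows if everyone switched near Day 701.
- SAP 7.6.2 models the AL002 groups "based on the integrated data up to Week 96 since the initiation of study treatment from both the Core Study and the LTE study". Alone this is weaker evidence, because the T-T Week 96 window runs to Day 771.

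The Week 48 lower end is a reading of these windows. The documents do not state it as a minimum.

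**The gap.** Gap in days = 701 − (Core Study Day of LTE Day 1), with LTE Day 1 taken as 28 days after the last Core dose.

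| Last Core dose | LTE Day 1 (Core day) | LTE Week 24 target: Core day (T-T label) | LTE Week 48 target: Core day (T-T label) | Gap to P-TC label |
|---|---|---|---|---|
| Week 48 | 365 | 533 (Week 72) | 701 (Week 96) | 48 weeks |
| Week 60 | 449 | 617 (Week 96) | 785 (Week 124) | 36 weeks |
| Week 72 | 533 | 701 (Week 96) | 869 (Week 124) | 24 weeks |
| Week 84 | 617 | 785 (Week 124) | 953 (Week 124) | 12 weeks |
| Week 96 | 701 | 869 (Week 124) | 1037 (Week 148) | 0 |

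A P-TC participant always gets Week 124 and Week 148. The labels differ by arm when LTE Day 1 is before Core Day 604 for the first visit (772 − 168) or before Core Day 618 for the second (954 − 336). Between Day 618 and Day 701 both arms get the same labels, and both sit somewhat before the target day.

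In the first row, the P-TC participant also has no Week 72 or Week 96 value, because those windows open at Days 422 and 590, after Day 365. The participant leaves the placebo/TC line and returns at Week 124 with 76-week data.

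**Direction.** With dosing capped at 96 weeks and a 4-week gap, an on-schedule P-TC visit can lag its label only by days but can precede it by many weeks.

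**Size in a plotted mean.** Bias against the label = share rolling over early × gap × decline rate. Share and rate are assumptions. Suppose a share s switches after a Week 48 last dose (gap 48 weeks), the rest after Week 96 (gap 0), and CDR-SB worsens by 1 to 2 points per year of 52.18 weeks:

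- s = 0%: no bias.
- s = 25%: mean gap 12 weeks; 12/52.18 × (1 to 2) = 0.23 to 0.46 points.
- s = 50%: mean gap 24 weeks; 0.46 to 0.92 points.
- s = 75%: mean gap 36 weeks; 0.69 to 1.38 points.

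**The case against.** The strongest reply is that the SAP mapping is a choice, not a slip. It aligns P-TC on the switch: labels through Week 96 hold pre-LTE data and later labels hold AL002 data. Simply re-windowing P-TC by Core day would put a participant who switched at Week 52 into Week 72 and Week 96 alongside participants still on placebo, so one placebo/TC line would mix exposures. With titration lasting 24 or 32 weeks (SAP 3.1), it would mix titration stages as well. This stands, and it limits which remedy is acceptable.

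The SAP also discloses both clocks, so a reader should not infer a hidden rule. Nor does it define a delayed-start objective or estimand. The early-versus-late-start comparison is one the plots invite, not one the plan tests.

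Four stronger readings are tempting, and the documents do not support them.

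- That every placebo participant is misplaced: the gap is zero when LTE Day 1 is Core Day 701.
- That efficacy inference is biased: the MMRM and pMMRM stop at Week 96 and use only Core and LTE-screening data for placebo (SAP 7.6.2, 7.7.3).
- That the ARIA comparison is affected: it uses the first 48 weeks of each study, and the MRI mapping in Table 7-12 is limited to volumetric results.
- That all biomarkers are flattered: target-engagement markers such as CSF sTREM2 may follow time since first AL002 dose, for which LTE day is the natural clock.

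**Conclusion.** The point holds for the Core-baseline tables and trend plots after Week 96, and only there. For a P-TC participant who rolls over before Core Day 701, the plotted visit precedes its label by the difference in days, up to about 48 weeks if Core dosing ended at Week 48. For steadily worsening measures such as CDR-SB, this makes placebo/TC look less declined than T-T at the same label.

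The direction rests on monotone progression and on some early roll-over taking place. The size is not established. A reader might take a figure such as 1 CDR-SB point as the bias in the plotted mean, but that needs both a large early roll-over share and an assumed decline rate, and the documents give neither. If nearly all placebo participants completed 96 weeks, the effect is negligible. Titration Cohort rows using LTE baseline are unaffected. This is worth correcting before the displays are programmed, because no other planned display compares these groups from Core baseline over that period.

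**What to change.** In displays based on Core baseline, do one of the following:

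1. Keep the switch-aligned visits, but plot post-switch placebo/TC points at their actual mean Core Study Day and report that day in the tables. This keeps placebo and AL002 exposure apart. It places the mean correctly if decline is roughly linear over the spread of days.
2. Show post-switch P-TC data as a separate line or row, windowed by Core Study Day with the T-T windows, and keep it out of the placebo column and the Week 96 models.

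Apply the same choice to volumetric MRI, plasma, CSF and PET under SAP 7.7.2. Keep LTE-day windows for rows that use LTE baseline. Tabulating the Core Study Day of LTE Day 1 would let readers judge the size of the effect.

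No new data are needed, since SAP 7.1.1.1 already continues Core Study Day into the extension for both groups. The cost is some extra programming and edits to the window tables or footnotes, plus a split line or fewer P-TC participants per late visit under the second option.
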